11.1 Primary Outcome

The primary outcome will be changes in cognitive functioning, measured by the CAMCOG-DS. This will be measured before the intervention, midway (10 weeks) and after the intervention (20 weeks). Both are continuous measures. Pre and post intervention scores in each group will be calculated as well as the mean difference in scores in the intervention arm and the control group.

11.2 Secondary outcome(s)

For all the secondary outcomes, we will explore changes in the mean scores and standard deviation pre and post intervention in each group, as well as between group differences.

- 1. Cognitive functioning measured using the memory for Objects test. This is a continuous measure.
- 2. Cognitive functioning measured using the CS-DS. This is a continuous measure.
- 3. Adaptive functioning will be measured using the ADCS-ADL. This is a continuous measure.
- 4. Quality of Life will be measured using the QOL-AD. This is a continuous measure.
- 5. Care giving burden will be assessed using the care Giving Burden Scale. This is a continuous measure.
- 6. The competence of dementia staff will be measured using the SCIDS. This is a continuous measure.
- 7. Anxiety and depression in carers will be measured using the Hospital Anxiety and Depression Scale. This is a continuous measure.

11.3 Sample size calculation

This is a feasibility study with no formal power calculation. There is no available data on the use of individual Cognitive Stimulation Therapy in the treatment of dementia in people with intellectual disability. This study may provide cautious estimates of changes in cognition as result of the intervention, which could then be used to power a larger randomised controlled trial. For a feasibility study, including 20 participants in each arm is considered to be an acceptable number.

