Exclusion criteria

- 1. Severe intellectual disabilities
- 2. Severe dementia
- 3. Visual or hearing impairment that prevents participation

Statistical methodology

As this is a feasibility study, we do not anticipate that there will be

and analysis:

statistically significant differences in the outcome measures between the intervention and control groups. However, we will examine differences in the mean and standard deviation for the primary outcome (cognitive functioning) in order to calculate a sample size for a larger study.

3 Background and Rationale

The prevalence of dementia in people with intellectual disabilities (ID) is almost five times higher when compared to the general population (1) and in people with Down syndrome, the prevalence is almost 90% (2) and is a significant cause of morbidity and mortality (3). Cognitive Stimulation Therapy (CST) has the strongest evidence for cognitive benefits in dementia (4). In the UK, the NICE guidelines (5) recommend that all people with mild/moderate dementia should be given the opportunity to participate in a structured group cognitive stimulation programme. Currently, people with ID and dementia are not offered CST, as no studies have examined its effectiveness in this group. CST significantly improves cognition and quality of life in people with dementia in the general population (6). It has comparable efficacy to anti-dementia drugs and is cost effective (7). Most of the evidence is based on group CST, typically two sessions a week lasting 45 minutes, over a seven week period (6). The intervention involves activities that include naming people and objects, word association, reminiscence, singing, creative activities, number and word games and discussion of current affairs. A range of evidence-based methods such as errorless learning, reality orientation and multi-sensory stimulation are used (8,9). The benefits of CST may arise from activation of neuronal networks associated with cognition such as memory and language (10).

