3.1 Assessment and Management of Risk

There will be no invasive tests or procedures that will be included above standard care. All the assessments will be based on standardised questionnaires. The intervention is not invasive.

The table below summarise the risks and mitigations of all test above standard care that are being performed in a table:

Intervention	Potential risk	Risk Management
Individual Cognitive Stimulation Therapy	Distress to participants	If participants are distressed by activities, the session should be terminated.
Administration of cognitive tests	Distress to participants	If participants are distressed, the session should be terminated.

4 Objectives

Primary:

To adapt and modify a manualised individual Cognitive stimulation (iCST) intervention for people with intellectual disabilities.

Secondary:

- 1. To carry out a feasibility randomised controlled trial to determine the tolerability and acceptability of the intervention (iCST) by examining the number of eligible participants, willingness of clinicians to recruit participants, willingness of participants to be randomised, appropriateness of outcome measures, drop-out rates, adherence to the intervention and acceptability of the intervention.
- 2. To determine the standard deviation and mean for the primary outcome measure (improvement in cognition in individuals with dementia and intellectual disability), which will be used to determine the sample size for a larger trial.

5 Trial design

The initial phase will involve the adaptation of the intervention and development of the iCST manual for people with intellectual disabilities and dementia.

1. Adaptation of the intervention (6 months in total)

The intervention will be modified according to the Medical Research Council guidelines on developing complex interventions (17). We will follow a similar procedure to that employed by the UCL group in developing the intervention and manual for iCST (18) and also their guidelines for adapting CST in other cultures (19).

Stage 1: focus groups and interviews (month 0-3)

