11.6.2 Primary outcome analysis

This is a feasibility study and therefore we are interested in examining the data in relation to recruitment. This will include information on how many participants were approached and agreed to be screened; how many met the eligibility criteria and agreed to take part and how many completed the study, or dropped out.

We do not anticipate that there will be any differences in between the intervention group and control with respect to the primary outcome as this is a feasibility study. We will calculate the changes in the mean and standard deviation between the two groups using Analysis of Covariance (ANCOVA), adjusting for the baseline score on the primary cognitive measure.

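### The larger trial is to be sized partly on the CAMCOG-DS effect observed with 20 per arm, an estimate too imprecise for that use; the target difference should be set independently

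*Protocol*

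**What the plan says.** Three places in the protocol link the pilot's results to the next sample size.

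- **Section 4, secondary objective 2.** The aim is "To determine the standard deviation and mean for the primary outcome measure", glossed as improvement in cognition, "which will be used to determine the sample size for a larger trial". This is a commitment.
- **Section 2, statistical methodology.** The team plans to look at "differences in the mean and standard deviation for the primary outcome (cognitive functioning) in order to calculate a sample size for a larger study". This is the only place that names the difference in means outright, and it is also firm.
- **Section 11.3.** The study may give "cautious estimates of changes in cognition as result of the intervention, which could then be used to power a larger randomised controlled trial". This is hedged.

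Section 11.3 also states "This is a feasibility study with no formal power calculation" and that "including 20 participants in each arm is considered to be an acceptable number". No minimum important difference on the CAMCOG-DS, or other target set apart from the pilot, appears anywhere.

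On the analysis, section 11.6.2 says "We will calculate the changes in the mean and standard deviation between the two groups using Analysis of Covariance (ANCOVA", with adjustment for the baseline score. Sections 2 and 11.6.2 both say that no significant difference, or no difference, is expected between the arms.

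**The concern.** A sample size needs a target difference and a standard deviation. A pilot of this size can give a usable, if loose, estimate of the SD. It cannot give a usable estimate of the effect, and the required N varies with the inverse square of that effect, so the error is magnified. A chance high estimate leads to an underpowered larger trial; a chance low one leads to an unaffordable N; an estimate at or below zero gives no superiority sample size at all. The protocol therefore plans to size the next trial partly on a quantity that it does not expect to detect.

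A smaller matter is that the SD to be carried forward is not tied to the planned analysis. ANCOVA does not estimate a change in SD between groups. It yields one adjusted mean difference and one residual SD, and that residual SD is what a larger trial analysed the same way needs.

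**Working it through.** **Inputs from the protocol.** 20 per arm, 40 in total (section 11.3); ANCOVA adjusted for baseline (section 11.6.2). The 20 per arm is not derived from a calculation, so there is no figure to reproduce.

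**Assumptions, not in the protocol.** Larger trial: two-sided alpha 0.05, power 80%, two equal arms. True effect d from 0.2 to 0.8 residual SD. All 40 complete, so the residual SD has 40 − 3 = 37 degrees of freedom; drop-out would widen every range below.

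**Step 1: precision of the observed effect.** SE(d) = √(2/20) = 0.316. With the t quantile on 37 df, the 95% interval is about ±0.64 residual SD.

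**Step 2: correct N at d = 0.3.** n = 2 × ((1.96 + 0.84)/0.3)² ≈ 175 per arm.

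**Step 3: chance of the wrong sign at d = 0.3.** Φ(−0.3/0.316) = Φ(−0.949) ≈ 17%.

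**Step 4: chance of a badly wrong N.** Because n is proportional to 1/d², N lies between half and double the correct value only if the observed effect lies between d/√2 and d√2. At d = 0.3 with the SD known:

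- limits 0.212 and 0.424, or z = −0.278 and 0.393
- probability inside = 0.653 − 0.391 = 0.262
- probability outside, wrong sign included = about 74%

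Simulating 400,000 pilots with the SD also estimated on 37 df gives:

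| True d (residual SD) | Wrong sign, or N below half or above double |
|---|---|
| 0.2 | 82% |
| 0.3 | 74% |
| 0.4 | 66% |
| 0.5 | 59% |
| 0.6 | 52% |
| 0.65 | 49% |
| 0.8 | 40% |

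At d = 0.3, among pilots with a positive estimate, the 10th to 90th percentile of the implied n per arm is about 27 to 1,890, against 175 needed.

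**Step 5: the same check with the target difference fixed independently.** N then varies only with the estimated residual variance. The 95% limits for the SD on 37 df are √(37/55.67) = 0.82 to √(37/22.11) = 1.29 times the estimate, so N × 0.66 to 1.67. N falls below half or above double the correct value in about 0.5% of pilots, whatever the true effect. True power falls below 70%, against 80% planned, in about 18%.

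**Step 6: which SD.** With equal variances at both visits and baseline correlation r (assumed), the residual variance is (1 − r²) times the raw variance and the change-score variance is 2(1 − r) times it. The inflation of N relative to the residual SD is therefore 2/(1 + r) for the change SD and 1/(1 − r²) for the raw SD:

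| r | Change SD | Raw SD |
|---|---|---|
| 0.5 | ×1.33 | ×1.33 |
| 0.7 | ×1.18 | ×1.96 |
| 0.8 | ×1.11 | ×2.78 |

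Both errors only oversize the trial.

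**The case against.** **The text is cautious.** Section 11.3 is hedged, objective 2 speaks of a mean rather than a difference in means, and nothing says that the observed effect would be the sole input or rules out a minimum important difference later. This stands as far as section 11.3 goes. But objective 2 and the Summary are not hedged, and the Summary names the difference in means.

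**The frequency depends on the assumed effect.** This stands. A reader might infer that the larger trial would be badly sized more often than not in all cases. The protocol gives no effect size from which to say so. By the half-or-double criterion the statement fails above about 0.65 residual SD; if only a wrong sign or true power below 70% counts, it fails above about 0.45. Small effects are nonetheless plausible on the protocol's own background, which reports no cognitive benefit of iCST in a trial of 356 dyads.

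**The choice of SD belongs in the SAP.** Largely fair, and the planned data will yield the residual SD. A reader might infer that N would nearly double through use of a raw SD. The text points rather to change scores (section 11.1 and objective 2), for which the inflation at r = 0.7 is 1.18. What remains is that section 11.6.2 misdescribes the output of ANCOVA.

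**No one will be misled into dropping the intervention.** A reader might infer that a null or negative estimate would end the programme. The protocol has no progression rule tied to the CAMCOG-DS effect; its feasibility criteria are recruitment, drop-out, adherence and acceptability.

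**Conclusion.** The concern holds for the use of the observed mean effect. Objective 2 and the Summary commit that effect to the next sample size, section 11.3 repeats the idea tentatively, and 20 per arm cannot support it. For assumed true effects of 0.2 to 0.6 residual SD, between 82% and 52% of pilots would give the wrong sign or an N wrong by more than a factor of two; at 0.8 it is still 40%. Setting the target difference independently brings this to about 0.5%.

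These figures rest on 80% power, two-sided 5% significance, full completion, and effects that the protocol does not state. The damage comes from the observed effect. The unspecified SD is a separate and secondary matter that can only oversize. The 20 per arm is not itself at fault: it is a conventional feasibility size and is not offered as powered. Nothing in this trial's conduct or participant safety is affected; the consequence falls on the larger trial.

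**What to change.** 1. In section 4 (secondary objective 2), section 2 and section 11.3, state that the larger trial will be powered on a minimum important CAMCOG-DS difference set independently of the effect observed here.
2. In the same places, state that this trial supplies the ANCOVA residual SD (or the SD together with the baseline to follow-up correlation), with its confidence interval, and the attrition rate. Attrition is already to be recorded.
3. State that the observed between-group difference will be reported with its 95% confidence interval and not used as the planning value.
4. In section 11.6.2, replace the reference to changes in mean and SD between groups with the baseline-adjusted mean difference and the residual SD.

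Planning on an upper confidence limit for the SD, rather than its point estimate, is one optional convention.

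The cost is wording in four places. Recruitment, visits, data collected and the ANCOVA itself do not change. The team must agree a minimum important difference before the larger trial is designed.

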11.4 Planned recruitment rate

We will be recruiting for ten months. We estimate that we will recruit four eligible participants each month from at least seven learning disability services in London. If recruitment is anticipated to be slow, we will recruit other centres if necessary.

11.5 Randomisation methods

We will be randomising participants (dyads comprising individuals with dementia and carers) to either the treatment or control arm. Randomisation will be based on varying block sizes and will be balanced to ensure an even distribution of participants taking cholinesterase inhibitors. There will be 20 participants in each arm. This will be carried out by a web-based package (Sealed Envelope).

11.6 Statistical analysis

11.6.1 Summary of baseline data and flow of participants

Following randomisation we will compare baseline characteristics in both groups to assess comparability. These will be gender, age, type of accommodation (family home, supported housing, residential or nursing home) carer status (informal or paid carer), mean scores on the primary outcome (Cognitive functioning, as measured by the CAMCOG-DS) and the mean number of people on anticholinesterase inhibitors.

We will produce a Consort Flow diagram to record the flow of participants in the trial, e.g. number of people who were screened and were eligible; the number of people who were randomised to each arm; the number of people who completed the first assessment (week 10-11); the number of people who completed the intervention or dropped out and the number of people who completed the final assessment (post intervention, 20-21 weeks).

11.6.2 Primary outcome analysis

This is a feasibility study and therefore we are interested in examining the data in relation to recruitment. This will include information on how many participants were approached and agreed to be screened; how many met the eligibility criteria and agreed to take part and how many completed the study, or dropped out.

We do not anticipate that there will be any differences in between the intervention group and control with respect to the primary outcome as this is a feasibility study. We will calculate the changes in the mean and standard deviation between the two groups using Analysis of Covariance (ANCOVA), adjusting for the baseline score on the primary cognitive measure.

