7.4 Concomitant medication (if applicable)

The participants will be permitted to take any medication that they usually take, including medication that may enhance cognition (e.g. acetyl cholinesterase inhibitors). These will be recorded carefully at baseline and follow up and considered in the analysis and interpretation of the data.

Concomitant medications will be recorded in the Participant's medical records/CRF.

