11.6.3 Secondary outcome analysis

As this is a feasibility study, we do not anticipate that there will be a statistically significant difference between the two groups in relation to the secondary outcomes. For each of the secondary outcomes, changes in the mean and standard deviation between the two groups will be calculated using Analysis of Covariance (ANCOVA), adjusting for the baseline score on the secondary outcome measure.

Other analyses:

The 40 recorded iCST sessions will be independently assessed by two raters for adherence to the manual. We will examine the carers' diaries to calculate the mean number of sessions that were completed by the carers and reasons for non-completion.

The qualitative interviews will be transcribed and analysed using thematic analysis to identify recurrent themes concerning participants' perceptions of the intervention. The findings will be used to further modify the intervention and to revise the manual.

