11.6.4 Sensitivity and other planned analyses

No sensitivity analysis will be conducted.

12 Record keeping and archiving

At the end of the trial, all essential documentation will be archived securely by the CI for a minimum of 20 years from the declaration of end of trial.

Essential documents are those which enable both the conduct of the trial and the quality of the data produced to be evaluated and show whether the site complied with all applicable regulatory requirements.

The sponsor will notify sites when trial documentation can be archived. All archived documents must continue to be available for inspection by appropriate authorities upon request.

13 Oversight Committees

There will be a Trial Management Group.

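### The ANCOVAs leave out cholinesterase-inhibitor use, the factor on which randomisation is balanced; the standard error and any residual SD will be somewhat too large if that factor predicts outcome beyond baseline

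*Protocol*

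**What the plan says.** Four places in the protocol bear on this.

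- Section 11.5 (randomisation): "Randomisation will be based on varying block sizes and will be balanced to ensure an even distribution of participants taking cholinesterase inhibitors". Also: "There will be 20 participants in each arm". Inhibitor use is the only factor named for balancing.
- Section 7.4 (concomitant medication), on usual medicines including those that may enhance cognition: "These will be recorded carefully at baseline and follow up and considered in the analysis and interpretation of the data". No model or covariate is named.
- Section 11.6.2 (primary outcome): the arms are compared by ANCOVA, "adjusting for the baseline score on the primary cognitive measure".
- Section 11.6.3 (secondary outcomes): ANCOVA again, "adjusting for the baseline score on the secondary outcome measure".

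Section 11.6.1 compares inhibitor use between arms at baseline, which is descriptive. Section 11.6.4 states: "No sensitivity analysis will be conducted". The summary (section 2) and the second secondary objective (section 4) say that the mean and SD of the primary outcome will be used to size a larger trial.

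**The concern.** A factor balanced by design contributes almost nothing to chance differences between the arms. If it also predicts outcome and is left out of the model, its variance is still counted in the residual. The model standard error then overstates the real sampling error of the treatment difference, and the residual SD is larger than that of a model containing the factor.

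The protocol pays for balance on inhibitor use and says this medication will be considered in the analysis, but no model it specifies does so. At stake are some precision in the estimated difference and, if the ANCOVA residual SD is the one carried forward, a somewhat larger sample size for the next trial.

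**Working it through.** The protocol gives no power, alpha, effect size or SD, so there is no stated figure to reproduce. The check compares the specified model with the same model plus the balancing factor.

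**Inputs from the protocol.** N = 40, 20 per arm; randomisation in varying blocks balanced on inhibitor use (read here as blocks within users and non-users); ANCOVA on arm and baseline score.

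**Inputs assumed.** The partial R² of inhibitor use given baseline and arm, from 0 to 0.20. For the simulation, 40% on inhibitors and blocks of 2 and 4. For the main-trial illustration, an effect of 0.5 baseline-adjusted SD, 80% power and two-sided 5%.

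**Degrees of freedom.** Arm + baseline: 40 − 3 = 37. Adding inhibitor use: 40 − 4 = 36.

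**Formulas (with the factor ÷ without it).**
- Residual SD ratio = √(1 − R²).
- 95% interval width ratio = √(1 − R²) × t(0.975, 36)/t(0.975, 37), where the ratio of t quantiles is 1.0009.
- Excess from omitting the factor = 1/√(1 − R²) − 1.
- Main trial per arm = 2(1.96 + 0.842)² × (1 − R²)/0.5², rounded up.

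Example at R² = 0.10: √0.90 = 0.949; excess 1/0.949 − 1 = 5.4%; width ratio 0.9487 × 1.0009 = 0.950; main trial 62.8 × 0.90 = 56.5, so 57 per arm.

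| Assumed partial R² | SD ratio | Interval ratio | Excess in SD if omitted | Main trial per arm, without → with factor |
|---|---|---|---|---|
| 0 | 1.000 | 1.001 | 0% | 63 → 63 |
| 0.05 | 0.975 | 0.976 | 2.6% | 63 → 60 |
| 0.10 | 0.949 | 0.950 | 5.4% | 63 → 57 |
| 0.20 | 0.894 | 0.895 | 11.8% | 63 → 51 |

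**What these strengths mean.** If users and non-users differ by d residual SDs after baseline adjustment and a proportion p are users, R² = d²p(1 − p)/[1 + d²p(1 − p)]. With p = 0.4, d = 0.5 gives 0.06/1.06 = 0.06, d = 0.8 gives 0.154/1.154 = 0.13, and d = 1.0 gives 0.24/1.24 = 0.19. A difference of d = 0.2 adds about 1% to the variance, or 0.5% to the SD. An R² of 0.20 is therefore a strong effect.

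**Coverage by simulation** (6,000 trials per scenario; Monte Carlo error about √(0.95 × 0.05/6000) = 0.3 percentage points).

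| Partial R² | Coverage without factor | Coverage with factor |
|---|---|---|
| 0 | 94.7% | 94.7% |
| 0.05 | 95.6% | 95.1% |
| 0.10 | 96.1% | 94.9% |
| 0.20 | 97.0% | 95.1% |

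**Break-even.** The factor pays for its degree of freedom once R² exceeds 1 − (1/1.0009)² ≈ 0.002.

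**The case against.** The strongest reply is that a reader might infer that the interval and the SD are too large as a matter of fact, and the documents do not support that. It depends on inhibitor use predicting follow-up CAMCOG-DS beyond the baseline score. No section gives a figure, and baseline may already carry most of the information. At R² = 0 the omission costs nothing. This stands, and the point is conditional for that reason.

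A reader might also infer that the SD handed to the larger trial is the ANCOVA residual SD. Sections 2 and 4 speak only of the mean and SD of the primary outcome, and a raw SD of scores or changes does not depend on covariates. Section 11.6.2 does speak of obtaining the SD through ANCOVA, which makes the residual SD a natural reading, but not the only one. Moreover, a baseline-only residual SD is the right input for a main trial analysed with baseline only. Section 11 names no confidence interval either.

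Nor does 11.6.4 rule out every further analysis; its sentence excludes sensitivity analyses. A statistical analysis plan, not shown, could spell out how 7.4 is to be met. That is fair, but the protocol itself names the method and its covariate, and that choice does not match 11.5 and 7.4.

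Finally, the effect is small beside the noise. With 37 degrees of freedom, the 95% limits on a residual SD are √(37/55.7) = 0.82 and √(37/22.1) = 1.29 times the estimate, or −18% to +29%, wider than the 0 to 12% at issue. That stands as a limit on importance. It is no reason to leave out a factor that costs almost nothing to include.

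**Conclusion.** The mismatch is real: randomisation is balanced on inhibitor use, section 7.4 says this medication will be considered in the analysis, and neither specified ANCOVA contains it. The consequence is conditional and modest. Over an assumed partial R² of 0 to 0.20, the standard error and any residual SD from the ANCOVA are too large by 0 to about 12%, and nominal 95% coverage is about 95% to 97%. Under the illustrative main-trial assumptions, 63 per arm would be planned where 63 to 51 would do, provided that trial is sized on this residual SD and itself adjusts for inhibitor use.

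Omission does not bias the treatment estimate, and the error is on the conservative side. The trial has no formal power calculation and expects no significant difference. For the carer outcomes (burden, competence, anxiety and depression) the gain may be slight. The omission and its direction are certain; its size is not known from the documents.

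**What to change.** In 11.6.2 and 11.6.3 write: 'ANCOVA adjusted for the baseline score and for cholinesterase-inhibitor use at randomisation (the balancing factor)'. This brings both sections into line with 11.5 and gives the statement in 7.4 a concrete form, at least for inhibitor use at baseline.

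The cost is a change of wording and one degree of freedom (37 to 36). The variable is already recorded at baseline and needed for randomisation. If it predicts nothing, the interval is about 0.1% wider.
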